10.6. Appendix 6: Values of Potential Clinical Importance

10.6.1. ECG

ECG Parameter	Units	Potential Clinically Important Range	
		Lower	Upper
Absolute			
Absolute QTc Interval	msec	> 450 ^[1]	
		> 450 ^[2]	≤ 479 ^[2]
		≥ 480 ^[2]	≤ 499 ^[2]
		≥ 500 ^[2]	
Absolute PR Interval	msec	< 110 ^[1]	> 220 ^[1]
Absolute QRS Interval	msec	< 75 ^[1]	> 110 ^[1]
Change from Baseline			
Increase from Baseline QTc	msec	≤ 30 ^[2]	
	msec	> 30 ^[1]	≤ 59 ^[2]
	msec	≥ 60 ^[2]	

NOTES:

1. Represent standard ECG values of PCI for HV studies.
2. Represent further subdivisions of ECG values for analysis.

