3.3.1. Risk Assessment

Potential Risk of Clinical Significance	Summary of Data/Rationale for Risk	Mitigation Strategy
Investigational Product (IP) Gepotidacin		
Gastrointestinal (GI) Effects	
Lower GI effects (soft stools, flatulence, and diarrhoea) are the most common GI-associated adverse events (AEs) reported in human participants dosed with gepotidacin.
 
In the Phase I studies, out of approximately 400 healthy participants who have received gepotidacin, Clostridium difficile has been reported in 8 participants.
	
Exclusion criterion and close monitoring of clinical parameters and AEs will be conducted to mitigate and assess GI effects.
 
Patients with significant GI symptoms will obtain the appropriate work-up (Appendix 5).
 
Participant evaluation criteria: Participants experiencing Grade 3 or Grade 4 AEs will be followed as appropriate until resolution of the AE (see Section 8.1.3).

Cardiovascular Effects Reversible increase in QT prolongation and a mild increase in heart rate in human participants.	In Study BTZ115775 (see GSK Document Number 2015N227098_00 Study ID BTZ115775), the infusion of gepotidacin at a dose of 1000 mg and 1800 mg over 2 hours caused a mild heart rate effect of approximately 6 bpm to 10 bpm and a QT prolongation, measured as $\Delta\Delta\text{QTcF}$, of 12 msec to 22 msec. The QT prolongation evolved during the infusion and was quickly reversed over 2 hours after the end of the infusion. Blood pressure observations were within normal ranges.	
Exclusion criteria, close monitoring of clinical parameters, and AEs will be conducted and stopping criteria will be utilized to mitigate and assess cardiovascular effects.
 
Note: Participants with baseline QTcF interval >450 msec (participant with normal hepatic function) or >480 msec (hepatically impaired participant) will be excluded.
 
Participant monitoring criteria: Participants experiencing a QTcB and/or QTcF >500 msec and/or a change from baseline in QTc >60 msec (see Section 8.1.2).

Potential Risk of Clinical Significance	Summary of Data/Rationale for Risk	Mitigation Strategy

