17. Participant with normal hepatic function has a baseline corrected QT interval using the Fridericia formula (QTcF) of >450 milliseconds (msec) and participant with hepatic impairment has a baseline QTcF of >480 msec.

Other Exclusions

18. Donation of blood in excess of 500 mL within 12 weeks prior to dosing or participation in the study would result in donation of blood or blood products in excess of 500 mL within a 56-day period.
19. Participant is unable to comply with all study procedures, in the opinion of the investigator.
20. The participant should not participate in the study, in the opinion of the investigator or Sponsor.

Supplemental Exclusion Criteria for Hepatically Impaired Participants

21. Participants with a pre-existing condition (except hepatic impairment) interfering with normal GI anatomy or motility that could interfere with the absorption, metabolism, and/or excretion of the study drugs. Participants with a history of inflammatory bowel disease should be excluded. Participants with a history of peptic ulceration or pancreatitis within the preceding 6 months of screening should be excluded.
22. Participants with any previous GI surgery (except appendectomy or gall bladder removal >3 months prior to Screening) may be enrolled in this study only if, in the opinion of the investigator and the medical monitor, it is not expected to interfere with the study procedures or to pose an additional safety risk to the participant.

23. Participants receiving lactulose who are medically unable to halt lactulose administration from 8 hours before dosing with study drug to 4 hours after dosing with study drug.
24. Participants with clinically active severe encephalopathy (grade 3 or 4 as defined in [Table 3](#)) as judged by the investigator or significant central nervous system disease (e.g., dementia or seizures) which the investigator considers will interfere with the informed consent, conduct, completion, or results of this trial or constitutes an unacceptable risk to the participant. Participants with a prior history of severe encephalopathy who are currently treated for this condition will receive the appropriate score for encephalopathy.

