9.4.3. Electrocardiograms

- Single 12-lead ECG will be obtained in a semi-supine position after 5 minutes rest as outlined in the SoA (Section 2) using an ECG machine that automatically calculates the heart rate and measures PR, QRS, QT, and QTc intervals. Refer to Section 8.1.2 for QTc evaluation criteria and additional QTc readings that may be necessary. Electrocardiograms should be obtained prior to any vital sign measurements or blood draws scheduled on the same assessment day.

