10.8.5. Safety Tables

Safety : Tables					
No.	Population	IDSL / Example Shell	Title	Programming Notes	Deliverable
Adverse Events					
2.1.	Safety	AE1	Summary of All Adverse Events by System Organ Class and Preferred Term		SAC
2.2.	Safety	AE1	Summary of Drug-Related Adverse Events		SAC
2.3.	Safety	AE15	Summary of Common (>=5%) Non-serious Adverse Events by System Organ Class and Preferred Term (Number of Subjects and Occurrences)		SAC
2.4.	Safety	AE16	Summary of Serious Adverse Events by System Organ Class and Preferred Term (Number of Subjects and Occurrences)		SAC
Laboratory Values					
2.5.	Safety	LB1	Summary of Clinical Chemistry Values Change from Baseline		SAC
2.6.	Safety	LB1	Summary of Hematology Values Change from Baseline		SAC
2.7.	Safety	UR3	Summary of Urinalysis Dipstick Results		SAC
Electrocardiograms					
2.8.	Safety	EG1	Summary of ECG Findings		SAC
2.9.	Safety	SAFE_T1	Summary of Frequency of Maximum Post-Dose ECG Parameter Corrected QTc Interval		SAC
2.10.	Safety	SAFE_T2	Summary of Frequency of Maximum Change from Baseline for ECG Parameter Corrected QTc Interval		SAC
2.11.	Safety	EG2	Summary of Change from Baseline in ECG Values		SAC
Vital Signs					
2.12.	Safety	VS1	Summary of Change from Baseline in Vital Signs		SAC

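### Table 2.9 counts QTc above 450 msec without regard to baseline, although impaired participants may enter with QTcF up to 480 msec

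*SAP*

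**What the plan says.** - **Flag.** SAP 10.6.1 marks an absolute QTc above 450 msec as potentially clinically important for all groups. Its note 1 reads "Represent standard ECG values of PCI for HV studies". The finer bands (above 450 to 479, 480 to 499, 500 and over) carry note 2, "Represent further subdivisions of ECG values for analysis". An increase above 30 msec also carries note 1.
- **Entry.** Protocol 6.2, exclusion 17, rules out controls with baseline QTcF above 450 msec. For the impaired groups the exclusion is that a "participant with hepatic impairment has a baseline QTcF of >480 msec".
- **Displays.** SAP 10.8.5 lists Table 2.9, "Summary of Frequency of Maximum Post-Dose ECG Parameter Corrected QTc Interval". Tables 2.10 and 2.11 cover change from baseline. SAP 10.8.8 adds Listing 31 (ECG values of potential clinical importance) and Listing 32 (all ECG values for any participant with such a value).
- **Readings.** Protocol 9.4.3: "Single 12-lead ECG will be obtained in a semi-supine position after 5 minutes rest". SAP 10.3.2 lets unscheduled readings into Tables 2.9 and 2.10. SAP 5.2 takes the Day 1 pre-dose ECG as baseline.
- **Known effect.** Protocol 3.3.1 reports a placebo-corrected QTcF increase "of 12 msec to 22 msec" after 2-hour infusions of 1000 mg and 1800 mg. No figure is given for the 1500 mg oral dose.

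**The concern.** ECG readings in impaired versus normal participants belong to a secondary safety objective (Protocol 4), for a drug with a recorded QT effect. Table 2.9 is the planned group display of long absolute QTc. Its lowest flagged class starts exactly at the control entry limit and 30 msec below the impaired entry limit. Impaired participants can therefore be counted as above 450 msec on the value they entered with, while controls should start at or below it. Taking the maximum of many single tracings also carries people just under the line across it.

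With about eight participants per group and descriptive reporting only, readers will take the counts at face value. An excess of long QTc in the impaired groups could be read as greater drug sensitivity when part of it was present before dosing.

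**Working it through.** The plan states no expected QTc frequency, mean or SD, so there is no figure of its own to reproduce.

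**Step 1: thresholds.** Flag minus control limit: 450 − 450 = 0 msec. Impaired limit minus flag: 480 − 450 = 30 msec. An impaired baseline of 451 to 479 msec falls in the first flagged band. One of exactly 480 msec falls in the second.

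**Step 2: number of readings.** The Protocol's Table 2 has post-dose ECGs at 1.5, 2, 4, 8, 12, 24, 36 and 48 h (8). Follow-up adds one: 8 + 1 = 9 scheduled, plus any unscheduled.

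**Step 3: effect of taking a maximum, no drug effect.** For a true QTc of *m* and within-participant SD *s* (assumed 5, 8 or 10 msec):

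P(max > 450) = 1 − Φ((450 − m)/s)^9

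Example, m = 440 and s = 8: Φ(1.25) = 0.894; 0.894^9 = 0.366; P = 0.63.

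| True QTc (msec) | s = 5 | s = 8 | s = 10 |
|---|---|---|---|
| 430 | 0.00 | 0.06 | 0.19 |
| 440 | 0.19 | 0.63 | 0.79 |
| 445 | 0.79 | 0.94 | 0.96 |
| 460 | 1.00 | 1.00 | 1.00 |

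Near or above the limit, the flag says little about drug.

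**Step 4: the same with a drug effect.** Take a peak effect *d* of 0, 12 or 22 msec, with assumed weights 1, 1, 0.6, 0.3, 0.1 and then 0 over the nine readings. The power in Step 3 becomes the product of Φ((450 − m − d × weight)/s). At m = 430 and s = 8, P is 0.06, 0.37 and 0.88. For baselines well below 450 msec the count does respond to drug.

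**Step 5: group level, no drug effect.** True QTc is taken as normal with between-participant SD 20 msec (assumed). Entry is decided on one screening reading with limit L = 450 or 480, so the weight at *m* is proportional to φ((m − mean)/20) × Φ((L − m)/s). Averaging the Step 3 formula over this weight, with mean 420 in both groups:

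| Within SD (msec) | Controls | Impaired | Difference |
|---|---|---|---|
| 5 | 7% | 13% | about 6 points |
| 8 | 12% | 19% | about 6 points |
| 10 | 17% | 23% | about 6 points |

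In a group of eight, 0.06 × 8 ≈ 0.5 participant. If the impaired mean were 440 msec instead, the impaired figure at SD 8 would be 52%. Nothing in the documents says that it is.

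**Step 6: group level with drug effect, SD 8, d = 0/12/22.** Controls at mean 420: 12%/23%/40%. Impaired at mean 440: 52%/65%/79%.

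**Step 7: what a split by baseline does.** With no drug effect, a new crossing (pre-dose reading at or below 450, maximum above) has probability Φ − Φ^10 at each *m*, with Φ taken at (450 − m)/s. Averaged as in Step 5 at mean 420, this is 5%, 9% and 13% in controls and 6%, 11% and 15% in impaired participants for SD 5, 8 and 10. The gap falls from about 6 points to 1 or 2. Crossings by noise remain: at an impaired mean of 440 they are 14% to 28%.

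**Step 8: a combined row, above 450 with a rise above 30 msec.** Control means of 410 and 420, impaired means of 420 to 440 and SD 5 to 10 give 0% to 7% with no effect, 0.2% to 17% at 12 msec and 6% to 39% at 22 msec. It gives few false alarms but misses most participants with an effect of the recorded size.

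**The case against.** A reader might infer that the above-450 count reflects only eligibility and noise, not drug. That goes too far. Steps 4 and 6 show the count rising with a 12 to 22 msec effect. An entry limit is also a ceiling: it does not say how many participants lie near it.

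A reader might also infer that the plan ignores baseline, or that new crossings cannot be identified at all. Neither is supported. An increase above 30 msec is itself a criterion of potential clinical importance, Tables 2.10 and 2.11 give change from baseline, and Listing 32 by its title shows every ECG value of each flagged participant. With at most 48 evaluable participants, the tracing can be done by hand. Safety is descriptive (Protocol 10.3.2), and no decision rule uses the above-450 count. The monitoring criteria in Protocol 8.1.2 are different ones.

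Two limits on the evidence also stand. The Table 2.9 shell is not shown, so a baseline row cannot be excluded. Exclusion 17 is stated in QTcF, whereas SAP 10.6.1 says only QTc and SAP 10.4.3 derives both QTcB and QTcF, so the comparison of limits is exact for QTcF only.

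What this does not answer: Tables 2.10 and 2.11 are separate marginal displays and do not show whether the participant above 450 msec is the one whose QTc rose. The 480 msec band does not resolve it either, because an impaired participant may enter at 480.

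**Conclusion.** The point holds for Table 2.9 as the SAP text describes it: the table does not separate pre-existing from new QTc prolongation, and its between-group comparison is confounded by baseline and eligibility. The threshold facts are exact for QTcF. The size is an illustration. The different entry limits alone add about 6 percentage points with no drug effect, given equal source means of 420 msec and the assumed SDs. The gap is larger only if impaired baselines are longer, which the documents do not state. Drug effect contributes to the count as well, and individual cases can be followed in Listing 32. This is a cheap improvement to a secondary safety display and not a flaw in the primary PK comparison.

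**What to change.** Make Table 2.9 a shift table by group: baseline QTcF class against maximum post-dose QTcF class, using the bands already in SAP 10.6.1 (450 or less, above 450 to 479, 480 to 499, 500 and over) and the Day 1 pre-dose baseline of SAP 5.2. Name QTcF explicitly. Exclusion 17 uses it, and Protocol 8.1.2 requires the eligibility formula to be kept for each participant's analysed QTc data. In Listings 31 and 32, mark any post-dose QTcF value whose class is higher than that participant's baseline class.

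A row for QTcF above 450 msec with an increase above 30 msec may be added as a supplement. It should not be the main measure, given its low sensitivity in Step 8. The shift table does not remove the upward pull of a maximum over nine or more single tracings, so it should still be read beside Table 2.10.

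Cost: SAP and shell wording, minor programming and one larger table. No new data are needed and no clinical rule changes.

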10.6.2. Vital Signs

Vital Sign Parameter (Absolute)	Units	Potential Clinically Important Range	
		Lower	Upper
Systolic Blood Pressure	mmHg	< 85	> 160
Diastolic Blood Pressure	mmHg	< 45	> 100
Heart Rate	bpm	< 40	> 110

10.7. Appendix 7: Abbreviations & Trade Marks

10.7.1. Abbreviations

Abbreviation	Description
ADaM	Analysis Data Model
AE	Adverse Event
Ae(t1-t2)	Amount of drug excreted in urine in a time intervals
Ae total	Total unchanged drug (total amount of drug excreted in urine)
AUC(0-∞)	Area under the concentration-time curve from time 0 (predose) extrapolated to infinite time
AUC(0-t)	Area under the concentration-time curve from time 0 (predose) to time of last quantifiable concentration
AUC(0-12)	Partial area under the curve estimated from urine concentrations samples collected from predose to 12 hours post dose
AUC(0-24)	Partial area under the curve estimated from urine concentrations samples collected from predose to 24 hours post dose
AUC(0-48)	Partial area under the curve estimated from urine concentrations samples collected from predose to 48 hours post dose
BMI	Body mass index
CDISC	Clinical Data Interchange Standards Consortium
CI	Confidence Interval
CL/F	Apparent oral clearance
CLr	Renal clearance of drug
Cmax	Maximum observed concentration
CVb	Coefficient of Variation (Between subjects)
DP	Decimal Places
ECG	Electrocardiogram
eCRF	Electronic Case Record Form
fe%	Percentage of the given dose of drug excreted in urine
FDA	Food and Drug Administration
GSK	GlaxoSmithKline
IA	Interim Analysis
ICH	International Conference on Harmonisation
IDSL	Integrated Data Standards Library
PCI	Potential Clinical Importance
PK	Pharmacokinetic(s)
QTcF	Frederica's QT Interval Corrected for Heart Rate
QTcB	Bazett's QT Interval Corrected for Heart Rate
RAP	Reporting & Analysis Plan
RAUC(0-t)	The ratio of the AUC(0-t) observed in saliva relative to the AUC(0-t) in plasma
RAUC(0-∞)	The ratio of the AUC(0-∞) observed in saliva relative to the AUC(0-∞) in plasma
SAC	Statistical Analysis Complete
SDTM	Study Data Tabulation Model
t1/2	Terminal phase half life

Abbreviation	Description
λ_z	Terminal-phase rate constant
TFL	Tables, Figures & Listings
t _{lag}	Lag time before observation of drug concentrations in sampled matrix
T _{max}	Time to first occurrence of C _{max}
V _z /F	Apparent volume of distribution of the terminal phase

10.7.2. Trademarks

Trademarks of the GlaxoSmithKline Group of Companies
NONE

Trademarks not owned by the GlaxoSmithKline Group of Companies
SAS
WinNonlin

10.8. Appendix 8: List of Data Displays

10.8.1. Data Display Numbering

The following numbering will be applied for RAP generated displays:

Section	Tables	Figures
Study Population	1.1 to 1.10	NA
Safety	2.1 to 2.12	NA
Pharmacokinetic	3.1 to 3.11	3.1 to 3.11
Section	Listings	
ICH Listings	1 to 40	
Other Listings	41 to 46	

10.8.2. Mock Example Shell Referencing

Non IDSL specifications will be referenced as indicated.

Section	Figure	Table	Listing
Study Population	POP_Fn	POP_Tn	POP_Ln
Safety	SAFE_Fn	SAFE_Tn	SAFE_Ln
Pharmacokinetic	PK_Fn	PK_Tn	PK_Ln

NOTES:

Non-Standard displays are indicated in the 'IDSL / Example Shell' or 'Programming Notes' column as '[Non-Standard] + Reference.'

10.8.3. Deliverables

Delivery	Description
IA	Interim Analysis (Part 1)
SAC	Final Statistical Analysis Complete

10.8.4. Study Population Tables

Study Population Tables					
No.	Population	IDSL / Example Shell	Title	Programming Notes	Deliverable
Subject Disposition and Populations					
1.1.	Enrolled	NS1	Summary of Number of Subjects Enrolled by Country and Site ID		SAC
1.2.	Safety	ES1	Summary of Subject Disposition for the Subject Conclusion Record		SAC
1.3.	Screened	ES6	Summary of Screening Status and Reasons for Screen Failures		SAC
1.4.	Screened	DV1	Summary of Important Protocol Deviations		SAC
Demographics					
1.5.	Safety	DM1	Summary of Demographic Characteristics		SAC
1.6.	Safety	DM5	Summary of Race and Racial Combinations		SAC
1.7.	Safety	DM6	Summary of Race and Racial Combinations Details		SAC
1.8.	Safety	DM11	Summary of Age Ranges		SAC
1.9.	Safety	POP_T1	Summary of Child-Pugh Scores		SAC
Medical Conditions and Concomitant Medications					
1.10.	Safety	MH4	Summary of Current Liver Disease and Cardiovascular Related Medical Conditions		SAC

10.8.5. Safety Tables

Safety : Tables					
No.	Population	IDSL / Example Shell	Title	Programming Notes	Deliverable
Adverse Events					
2.1.	Safety	AE1	Summary of All Adverse Events by System Organ Class and Preferred Term		SAC
2.2.	Safety	AE1	Summary of Drug-Related Adverse Events		SAC
2.3.	Safety	AE15	Summary of Common (>=5%) Non-serious Adverse Events by System Organ Class and Preferred Term (Number of Subjects and Occurrences)		SAC
2.4.	Safety	AE16	Summary of Serious Adverse Events by System Organ Class and Preferred Term (Number of Subjects and Occurrences)		SAC
Laboratory Values					
2.5.	Safety	LB1	Summary of Clinical Chemistry Values Change from Baseline		SAC
2.6.	Safety	LB1	Summary of Hematology Values Change from Baseline		SAC
2.7.	Safety	UR3	Summary of Urinalysis Dipstick Results		SAC
Electrocardiograms					
2.8.	Safety	EG1	Summary of ECG Findings		SAC
2.9.	Safety	SAFE_T1	Summary of Frequency of Maximum Post-Dose ECG Parameter Corrected QTc Interval		SAC
2.10.	Safety	SAFE_T2	Summary of Frequency of Maximum Change from Baseline for ECG Parameter Corrected QTc Interval		SAC
2.11.	Safety	EG2	Summary of Change from Baseline in ECG Values		SAC
Vital Signs					
2.12.	Safety	VS1	Summary of Change from Baseline in Vital Signs		SAC

10.8.6. Pharmacokinetic Tables

Pharmacokinetic : Tables					
No.	Population	IDSL / Example Shell	Title	Programming Notes	Deliverable
PK Concentration Data					
3.1	PK Concentration	PKCT1	Summary of Gepotidacin Plasma Pharmacokinetic Concentration-Time Data (units) by Hepatic Function Group		IA, SAC
3.2	PK Concentration	PKCT1	Summary of Gepotidacin Urine Pharmacokinetic Concentration-Time Data (units) by Hepatic Function Group		IA, SAC
3.3	PK Concentration	PKCT1	Summary of Gepotidacin Saliva Pharmacokinetic Concentration-Time Data (units) by Hepatic Function Group		IA, SAC
PK Parameters Tables					
3.4	PK Parameter	PKPT4	Summary of Derived Gepotidacin Plasma Pharmacokinetic Parameters by Hepatic Function Group	Parameters with units. If Group E are enrolled in part 2, then include a page of part 1 (Group B and D) alone in SAC deliverable as a reference for part 1 IA.	IA, SAC
3.5	PK Parameter	PKPT4	Summary of Derived Gepotidacin Urine Pharmacokinetic Parameters by Hepatic Function Group	Parameters with units.	IA, SAC
3.6	PK Parameter	PKPT4	Summary of Derived Gepotidacin Saliva Pharmacokinetic Parameters by Hepatic Function Group	Parameters with units.	IA, SAC

Pharmacokinetic : Tables					
No.	Population	IDSL / Example Shell	Title	Programming Notes	Deliverable
PK Analysis Tables					
3.7	PK Parameter	PKPT3	Statistical Analysis of Gepotidacin Plasma Pharmacokinetic Parameters: Analysis of Variance (ANOVA)	AUC(0-∞) and Cmax only by Hepatic Function Group. If Group E are enrolled in part 2, then include a page of part 1 (Group B and D) alone in SAC deliverable as a reference for part 1 IA.	IA, SAC
3.8	PK Parameter	PKPT3	Statistical Analysis of Gepotidacin Urine Pharmacokinetic Parameters: Analysis of Variance (ANOVA)	AUC(0-48) and CLr only by Hepatic Function Group.	IA, SAC
3.9	PK Parameter	PKPT3	Statistical Analysis of Gepotidacin Saliva Pharmacokinetic Parameters: Analysis of Variance (ANOVA)	AUC(0-∞) and Cmax only by Hepatic Function Group.	IA, SAC
3.10	PK Parameter	PK T1	Statistical Analysis of Gepotidacin Plasma Tmax		IA, SAC
3.11	PK Parameter	PK T1	Statistical Analysis of Gepotidacin Saliva Tmax		IA, SAC

10.8.7. Pharmacokinetic Figures

Pharmacokinetic : Figures					
No.	Population	IDSL / Example Shell	Title	Programming Notes	Deliverable
Concentration Plots					
3.1	PK Concentration	PKCF1P	Individual Gepotidacin Plasma Concentration-Time Plots by Hepatic Function Group (Linear and Semi-Logarithmic)	Dashed line represents the LLQ. Present all hepatic function groups in the same plots.	IA, SAC
3.2	PK Concentration	PKCF1P	Individual Gepotidacin Urine Concentration-Time Plots by Hepatic Function Group (Linear and Semi-Logarithmic)	Dashed line represents the LLQ. Present all hepatic function groups in the same plots. Plot concentration at the collection midpoint.	IA, SAC
3.3	PK Concentration	PKCF1P	Individual Gepotidacin Saliva Concentration-Time Plots by Hepatic Function Group (Linear and Semi-Logarithmic)	Dashed line represents the LLQ. Present all hepatic function groups in the same plots.	IA, SAC
3.4	PK Concentration	PKCF2	Mean Gepotidacin Plasma Concentration-Time Plots (Linear and Semi-Logarithmic)	Dashed line represents the LLQ. Present all treatment groups in the same plots.	IA, SAC
3.5	PK Concentration	PKCF2	Mean Gepotidacin Urine Concentration-Time Plots (Linear and Semi-Logarithmic)	Dashed line represents the LLQ. Present all treatment groups in the same plots. Plot concentration at the collection midpoint.	IA, SAC
3.6	PK Concentration	PKCF2	Mean Gepotidacin Saliva Concentration-Time Plots (Linear and Semi-Logarithmic)	Dashed line represents the LLQ. Present all treatment groups in the same plots.	IA, SAC

Pharmacokinetic : Figures					
No.	Population	IDSL / Example Shell	Title	Programming Notes	Deliverable
3.7	PK Concentration	PKCF3	Median Gepotidacin Plasma Concentration-Time Plots (Linear and Semi-Logarithmic)	Dashed line represents the LLQ. Present all treatment groups in the same plots.	IA, SAC
3.8	PK Concentration	PKCF3	Median Gepotidacin Urine Concentration-Time Plots (Linear and Semi-Logarithmic)	Dashed line represents the LLQ. Present all treatment groups in the same plots. Plot concentration at the collection midpoint.	IA, SAC
3.9	PK Concentration	PKCF3	Median Gepotidacin Saliva Concentration-Time Plots (Linear and Semi-Logarithmic)	Dashed line represents the LLQ. Present all treatment groups in the same plots.	IA, SAC
Exploratory Objectives					
3.10	PK Concentration	PK_F4	Scatter Plot of Gepotidacin Saliva and Unbound Plasma Concentrations by Hepatic Function Group	Present all treatment groups in the same plots.	IA, SAC
3.11	PK Parameter	PK_F5	Scatter Plot of Gepotidacin Saliva and Unbound Plasma PK Parameters by Hepatic Function Group	Present all treatment groups in the same plots. Repeat for PK parameters AUC(0-t), AUC(0-inf), Cmax, CL/F and t _{1/2} .	IA, SAC
3.12	PK Concentration	PK_F4	Scatter Plot of Gepotidacin Saliva and Total Plasma Concentrations by Hepatic Function Group	Present all treatment groups in the same plots.	IA, SAC
3.13	PK Parameter	PK_F5	Scatter Plot of Gepotidacin Saliva and Total Plasma PK Parameters by Hepatic Function Group	Present all treatment groups in the same plots. Repeat for PK parameters AUC(0-t), AUC(0-inf), Cmax, CL/F and t _{1/2} .	IA, SAC

